- baseline and follow-up nighttime CGM metrics.

134 5.7.4 CGM Metrics by Study Week and Infusion Set Wear

- 24-hour CGM metrics will be calculated for each week of the study and each infusion set wear.
- 136 A minimum of 72 hours is required to calculate CGM metrics for these periods.

137 5.7.5 CGM Metrics during the Final 14 Days of the Study

- 138 24-hour CGM metrics from the final 14 days of the study will be tabulated and compared with
- baseline. Participants must complete at least six wear periods to be included in these analyses. A
- minimum of 144 hours is required to calculate CGM metrics for this period.

141 5.7.6 Hyperglycemia Trend over Duration of Wear

- The trend in hyperglycemia will be assessed with CGM metrics % time above 180 mg/dL, %
- time above 250 mg/dL, and mean glucose.
- Hyperglycemia trend outcomes will be tabulated by day of infusion set wear. A minimum of 20
- hours of data is required for a day to be included in these tabulations.

- 146 Hyperglycemia trend outcomes will also be tabulated by period of the wear (hours 0–<72 versus
- hours 72–168 since infusion set insertion). They will be compared between hours 0–<72 and
- hours 72–168. A minimum of 48 hours in both periods is required to calculate CGM metrics.

149 5.7.7 Prolonged Hyperglycemic Events

- 150 A CGM-measured hyperglycemic event will be defined as at least 2 sensor values >250 mg/dL
- that are 120 or more minutes apart plus no intervening values ≤250 mg/dL; at least 2 sensor
- values ≤180 mg/dL that are 15 or more minutes apart with no intervening values >180 mg/dL are
- required to define the end of an event, at which point the study participant becomes eligible for a
- 154 new event.

155 **5.7.8** Hypoglycemic Events

- 156 A CGM-measured hypoglycemic event <54 mg/dL will be defined as at least 2 sensor values
- 157 <54 mg/dL that are 15 or more minutes apart plus no intervening values ≥54 mg/dL; at least 2

- sensor values ≥54 mg/dL that are 15 or more minutes apart with no intervening values <54
- mg/dL are required to define the end of an event, at which point the study participant becomes
- 160 eligible for a new event.

161 5.8 Calculation of Insulin Metrics

- 162 For each insulin metric, one value will be calculated for each participant. Tandem pumps
- automatically generate basal records approximately every 5 minutes, and 20 hours of data per
- day will be required for a day to be considered complete. Only data from the study pump during
- wears of the investigational infusion set will be included; all data from a personal pump (if used
- during the study) will not be counted. Any dropouts will be counted as zero use for the remainder
- of the study.

168 **5.8.1 Overall**

- Overall insulin metrics will be calculated over the entire follow-up period. A minimum of 21
- 170 complete days are required to calculate total daily insulin metrics. Baseline insulin delivery will
- be obtained from the Demographics CRF, which describes the week prior to the Screening visit.

172 5.8.2 Insulin Metrics by Study Week

- 173 Insulin metrics will be calculated for each week of the study. A minimum of 6 complete days of
- insulin data is required to calculate insulin metrics for a week.

175 5.8.3 Insulin Metrics by Day of Infusion Set Wear

- 176 Insulin metrics will also be tabulated by day of infusion set wear over the entire study. A day is
- each subsequent 24-hour period since the current set is inserted. Participants must provide a
- minimum of six complete days of insulin data to be included in the calculation for insulin metrics
- on that day.

180 **6 Description of Statistical Methods**

181 **6.1 Analysis Cohorts**

- Analysis of the Primary Efficacy endpoint will include participants who successfully insert at
- least one investigational infusion set.
- 184 The analysis of the Key Secondary endpoint and the safety endpoints will include all participants
- who attempt to insert at least one investigational infusion set.
- Analyses of all other endpoints will include participants who successfully insert at least one
- investigational infusion set. Intention-to-treat is not relevant since this is not a randomized trial.

188 **6.2** Analysis of the Primary Endpoint

- The proportions of successfully inserted investigational infusion sets that last at least 7 days will
- be tabulated overall and by infusion set location. Reasons reported for removal (main and
- secondary) will be tabulated. All tabulations will be done separately for each insulin type
- 192 (Humalog and Novolog).
- Analysis will be done separately for each insulin type. Kaplan-Meier estimates will be reported
- along with a curve used to estimate the proportion of infusion sets that last at least 7 days.
- 195 Successfully inserted infusion sets that are removed prior to day 7 without meeting the stated
- 196 failure criteria in section 5.2 (Primary Efficacy Endpoint) will be treated as censored
- observations at the times reported. A two-sided 95% confidence interval (95% CI) for the 7-day
- survival rate will be calculated with a bootstrap to account for the correlated data from having
- each participant wear multiple infusion sets. A corresponding bootstrap p-value will be given for
- 200 the null hypothesis that the true survival probability is 75%.
- There will be no imputation of missing data for the primary analysis.

202 6.3 Analysis of the Secondary Endpoints

- 203 If results from the Primary Efficacy and Key Secondary analyses are comparable for Humalog
- and Novolog, then the data will be pooled for the other Secondary, Exploratory, and Safety
- analyses. Otherwise, separate analyses will be done by insulin type.

206 **6.3.1 SteadiSet IIS Success Rate**

- 207 Percentage of SteadiSet infusion sets not withdrawn from use prior to 7 days (168 hours) as
- 208 evidenced by the absence of device failure as defined in section 5.3 (Key Secondary Endpoint)
- will be analyzed using the same statistical methods as described above for the Primary Efficacy
- 210 endpoint. Successfully inserted infusion sets that are removed prior to day 7 without meeting the
- stated failure criteria in section 5.3 will be treated as censored observations at the times reported.

212 6.3.2 CGM Endpoints

- 213 Baseline and follow-up secondary CGM-measured glycemic metrics will be compared. Each
- 214 metric will have summary statistics appropriate to its distribution tabulated. A paired t-test will
- be used to compare the baseline and follow-up values from the final 14 days of the study and

- 216 from the entire duration of study set wear, and a two-sided 95% CI will be given for the mean
- difference. Boxplots will be drawn at baseline and follow-up, and scatter plots will be drawn for
- baseline versus follow-up. Participants will be included in the analysis only if they have both
- baseline and follow-up values. If the paired differences appear skewed, a signed rank test will be
- 220 used instead.
- 221 If these analyses are performed separately by insulin type, endpoints over the entire follow-up
- period will be categorized according to the insulin type in use at baseline and any wear during
- 223 which more than one insulin type is used will be included in the calculation. Participants must
- use the same insulin type as they used at baseline for the final 14 days of follow-up to be
- included in the comparison of the final 14 days to baseline.

226 **6.3.2.1** Daytime and Nighttime

- Baseline and follow-up summary statistics for CGM-measured outcomes will be tabulated by
- time of day (daytime or nighttime). 24-hr profile plots will be drawn for follow-up. If these
- analyses are performed separately by insulin type, endpoints over the follow-up period will be
- categorized according to the insulin type in use at baseline and any wear during which more than
- one insulin type is used will be included in the calculation.

232 6.3.2.2 Hyperglycemia Trend over Duration of Wear

- Tables of statistics appropriate to their distributions will summarize hyperglycemia trend
- outcomes by day of infusion set wear.
- Summary statistics will be tabulated for hours 0–<72 and hours 72–168 of infusion set wear.
- Boxplots will be drawn for hours 0–<72 and 72–168. A paired t-test will be used to compare the
- 237 0–<72 hour and 72–168 hour values, and a two-sided 95% CI will be given for the mean
- 238 difference. Participants will be included in the analysis only if they have both 0–<72 hour and
- 239 72–168 hour values. If the paired differences appear skewed, a signed rank test will be used
- 240 instead.

241 **6.3.3** Insulin Endpoints

- 242 Summary statistics appropriate to their distributions will be tabulated at baseline and follow-up
- 243 for all secondary insulin outcomes: total daily insulin, total basal insulin, total bolus insulin, and
- bolus/basal ratio. Boxplots will be drawn at baseline and follow-up. Insulin endpoints will also
- be tabulated by study week and by day of infusion set wear.

246 **6.3.4 Pump Endpoints**

- 247 Summary statistics for pump occlusion alarm rates will be reported overall and by day of
- infusion set wear. If tables are constructed separately by insulin type, results will be categorized
- according to the insulin type in use at baseline and any wear during which more than one insulin
- 250 type is used will be included in the calculation.

251 6.3.5 Tolerability Endpoints

- 252 Pain assessment results will be tabulated overall and by infusion set wear, and appropriate
- summary statistics will be reported. If tables are constructed separately by insulin type, results

- over the follow-up period will be categorized according to the insulin type in use at baseline and
- any wear during which more than one insulin type is used will be included in the calculation.

256 **6.4** Analysis of the Exploratory HbA1c Endpoint

- 257 Summary statistics appropriate to the distributions will be tabulated for baseline and follow-up
- 258 HbA1c values. A paired t-test will compare the central lab HbA1c values measured at the final
- study visit versus the Day 0 value, and a two-sided 95% CI will be given for the mean difference.
- 260 Participants will be included in the analysis only if they have a central lab value at both times. If
- 261 the paired differences appear skewed, a signed rank test will be used instead. Boxplots will be
- drawn at baseline and follow-up, and scatter plots will be drawn for baseline versus follow-up.
- 263 If analyses are performed separately by insulin type, results over the follow-up period will be
- 264 categorized according to the insulin type in use at baseline.

265 6.5 Usability, Satisfaction & Preference Survey

- Survey responses will be tabulated for each of the three visits, and appropriate summary statistics
- will be reported.
- The following comparisons will be made between survey results: the 2-Week visit versus
- baseline, the Final visit versus baseline, and the Final visit versus the 2-Week visit. The System
- Usability Scale portion of the questionnaire will be scored according to published guidelines¹
- and compared between surveys as a single unit. Other questions will be converted to a 0–100
- scale and corresponding questions will be compared between surveys individually. Differences
- will be analyzed with paired t-tests or signed rank tests, as appropriate. Ninety-five percent
- 274 confidence intervals will be derived from these tests.
- 275 If these analyses are performed separately by insulin type, results over the follow-up periods will
- be categorized according to the insulin type in use at baseline.

7 Safety Analyses

- All enrolled participants will be included in the safety analyses and all their adverse events up to
- the end of the study will be listed.
- Adverse events will be tabulated overall and by wear period, which will be from the time of
- insertion until the time of the next insertion. Adverse events reported after the final wear period
- will be assigned to the final wear period. Whether or not the adverse event occurred while the
- study infusion set was being used will be indicated as will the relationship of adverse events to
- 284 the study device. Any AE involving hyperglycemia/ketosis will include an assessment of
- 285 whether it corresponded to an infusion set failure. The circumstances of all reportable adverse
- events will be summarized.

287

8 Intervention Adherence and Retention Analyses

- The following tabulations and analyses will be performed overall and by insulin type to assess
- intervention adherence, protocol adherence, and retention:

- Flowchart of study participants
- Number of investigational infusion sets worn
- Gaps of ≥3 hours in infusion set wears
- Tabulation of infusion set removal cases reviewed by the CEC and their determinations
- Distribution of infusion set wear per participant
- Visit completion rates for each follow-up visit
- Protocol deviations
- Numbers of and reasons for unscheduled visits and phone calls
- Participant adherence to expected BG/ketone/correction bolus procedures prior to set removals before 7 days

9 Baseline Descriptive Statistics

- 301 Baseline demographic and clinical characteristics of the cohort of all enrolled participants with at
- least one wear will be summarized in a table. For continuous variables, appropriate summary
- statistics will be given. For discrete variables, number and percentage will be reported for each
- 304 category.

300

- The following baseline characteristics will be included in the table:
- 306 Age
- 307 Sex
- 308 Race/ethnicity
- Diabetes duration
- Education
- Household Income
- Health Insurance
- 313 ◆ HbA1c
- 314 BMI

322

- CGM metrics
- \circ % Time >180 mg/dL
- \circ % Time < 70 mg/dL
- o Estimated HbA1c
- Insulin type—Humalog or Novolog
- Infusion set type in use at time of study screening

10 Planned Interim Analyses

No formal interim efficacy analyses are planned for this study.

324 11 Subgroup Analyses

- 325 The Primary Efficacy and Key Secondary outcomes as well as CGM hyperglycemia metrics (%
- 326 time > 180 mg/dL, % time > 250 mg/dL, mean glucose), HbA1c, and insulin metrics will be
- 327 explored according to the factors below.
- Hours 0–<72 versus hours 72–168 since infusion set insertion
- Infusion set location
- Whether any additional taping and/or skin adhesive barrier wipe was used to secure the infusion set on the day that it was inserted
- Units per day of insulin (<25 versus ≥25)
- Diabetes duration

334

335

336

337

351

352

353

354

355

356

357

358

359

360

- Participants who manually stop the insulin pump more often; only participants who successfully insert at least 6 infusion sets will be included, and the number of stops will be averaged over every day of the study for which data is complete as defined in 5.8.
 - o Cut point will be chosen according to the distribution of the data
- 338 Hypothesis tests for differences between subgroups among the Primary Efficacy, Key
- 339 Secondary, and CGM outcomes will be performed. Difference in HbA1c will be tested between
- 340 subgroups based on units per day of insulin, diabetes duration, and how often participants stop
- 341 the insulin pump. When subgroups are based on categorical variables, comparisons will only be
- made when each subgroup contains at least five members. Cut points for diabetes duration will
- be chosen according to the distribution of the data, but it will be treated as a continuous variable
- in the models.
- Pump occlusion alarms will be tabulated by units per day of insulin and frequency of manual
- pump interruption but no formal comparisons will be made.

347 12 Multiple Comparisons

- No correction will be made for the Primary Efficacy analysis or the Key Secondary analysis. For
- other analyses, the false discovery rate (FDR) will be controlled using the adaptive Benjamini-
- Hochberg procedure². The categories for FDR correction will be:
 - HbA1c and CGM outcomes
 - o Entire follow-up period versus baseline
 - CGM outcomes
 - o Final 14 Days versus baseline
 - Subgroups
 - o Primary and Key Secondary outcomes
 - Hours 0–<72 versus hours 72–168
 - Infusion set location
 - <25 units/day of insulin

 - Participants who start and stop the insulin pump more often
- Whether any additional taping and/or skin adhesive barrier wipe was used to secure the infusion set on the day that it was inserted

363	 Diabetes duration
364	 HbA1c (where applicable) and CGM outcomes
365	■ Hours 0–<72 versus hours 72–168
366	Infusion set location
367	<25 units/day of insulin (HbA1c applicable)
368	 Participants who start and stop the insulin pump more often (HbA1c
369	applicable)
370	 Whether any additional taping and/or skin adhesive barrier wipe was used
371	to secure the infusion set on the day that it was inserted
372	 Diabetes duration (HbA1c applicable)
373	 Usability, Satisfaction & Preference Survey

13 Additional Tabulations and Analyses

- The numbers and percentages of participants and wears will be reported for each insertion
- 376 location.

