398 399 400 401 402	at the dinvestiguisits v	reening visit and subsequent scheduled study visits may be conducted virtually via videoconference iscretion of the study investigator, for example due to institutional restrictions or the subject or gator's preference for a remote visit. Study staff will discuss the feasibility of conducting virtual with each subject and provide support as needed to ensure adequate access. The initial screening last be completed within 30 days of subject enrollment (i.e., completion of consent documentation).
403		2.5 Historical Information
404 405 406	the sub	ry will be elicited from the subject and extracted from available medical records with respect to ject's diabetes history, current diabetes management, other past and current medical problems, d current medications, and drug allergies.
407 408 409	from th	evaluating subjects not already being treated at the enrolling clinic, information will be solicited e subject's primary diabetes provider, for example, via a phone call or videoconference between olling investigator and the current provider.
410		2.6 Screening Testing and Procedures
411	At the	Screening Visit the following procedures will be performed/information will be elicited:

412	 Assessment of eligibility
413	 Demographics (date of birth, gender, race, and ethnicity)
414 415	 Contact information (retained at the site and provided to Coordinating Center to allow automated text or email messages during study)
416	 Medical history as described above in Section 2.4
417	 Substance use history (drinking, smoking, and drug habits)
418	 Current medications
419	 Measurement of height/weight
420 421	 If the visit is conducted virtually, a verbal report of the subject's weight and verbal report of height will be acceptable.
422 423	 Urine pregnancy test for all women who have reached menarche and are premenopausal and are not surgically sterile.
424 425	 If the visit is conducted virtually, a negative urine pregnancy test result from a test kit sent to the subject may be confirmed via teleconference.
426 427	 Determination of adherence to Control-IQ use in the 14 days prior to screening based on data from the subject's personal t:connect account.
428 429	 Subjects must have had Control-IQ technology active at least 85% of the time during the 14 days before screening to be eligible to continue in the study.
430	 Verification HbA1c is <9.0% in the last 6 months.

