479 Subjects will be instructed to insert a new sequential infusion set following removal of each prior set until 12 infusion sets have been used. Sets that fail in the first 8 hours of use will be replaced 480 and will not count toward the target of 12 infusion sets worn. 481 Subjects will be instructed to change the insulin cartridge every 48-72 hours, as recommended by 482 their healthcare provider. 483 484 Subjects will be instructed to change their insulin cartridge and infusion set independent of each other and follow instructions in the Participant Guidebook and IFU. Subjects will be instructed to 485 contact study site if there is concern about infusion set failure. 486 Subjects will be required to upload insulin pump data (which includes both insulin dosing and 487 CGM data). This will be performed remotely for virtual visits or in clinic for face-to-face visits. 488 Ketone and BG meters will be uploaded during face-to-face visits. 489 Subjects who have only virtual visits will be provided with three ketone and BG meters each, and 490 will be instructed to mail the meters to the study site at week 2, week 6 and final visits. 491 3.2 Hyperglycemia Management Guidelines 492 The study pump's Control-IQ High Alert, which cannot be disabled, will alert the subject when there is 493 a CGM reading >200 mg/dL and no prediction the CGM will decrease in the next 30 minutes. 494 495 The study pump's optional CGM High Alert will be configured by study staff with a threshold of 250 mg/dL and a Repeat setting of 60 minutes, so the alert recurs every 60 minutes as long as the 496 hyperglycemia persists. High BG reminder should be set to OFF. 497 The pump will have the "out of range" alert set for 20 minutes (shortest possible setting) to reduce risk of 498 499 missing data. The pump "low insulin alert" will be set at ≥ 20 units to reduce risk of running the pump on an empty cartridge. It is recommended to set the Auto Off Alert to OFF. Site Reminder alert may be set to 500 ON to remind subjects to change their cartridge but not their infusion set. 501 502 Subjects will be instructed not to modify the alert settings configured by study staff that are described above. 503 Subjects will receive training on how to address Occlusion alarm #1 (resolvable alarm) and Occlusion 504 alarm #2 (non-resolvable alarm) requires infusion set change. 505 Study subjects will be provided a written Hyperglycemia Management Guidelines that will specify the 506 steps to take in case of prolonged hyperglycemia, testing of blood glucose, ketones, and correction 507 boluses. 508 509 3.3 Hypoglycemia Management Hypoglycemia will be managed by the Study subjects as they would as part of their usual diabetes 510 management. Hypoglycemia alarms may be set at the discretion of the study subject. 511 3.4 Daily Text 512 Subjects will receive a daily reminder text indicating the target date and time of infusion set removal. 513 The daily text will provide a link to a questionnaire for the subject to complete with each infusion set 514 insertion and removal providing specifics about all infusion set changes. 515 3.5 Follow-up Visit and Contact Schedule 516 517 Subjects will have the following scheduled follow-up visits and phone contacts as follows:

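### The frequent-stops subgroup in SAP 11 is built from pump stops during the study, with no exclusion for stops caused by set changes or failures, so set failures can raise the stop rate that defines the group.

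*SAP*

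**What the plan says.** Set performance in people who often stop and start the pump is item 5 of the other secondary endpoints (Protocol 1.3.4 and 8.4.5). The protocol does not say what counts as frequent.

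SAP section 11 supplies the definition. Manual stops are counted during the study, and "the number of stops will be averaged over every day of the study for which data is complete as defined in 5.8". The analysis is restricted: "only participants who successfully insert at least 6 infusion sets will be included". For the split, "Cut point will be chosen according to the distribution of the data". The section then plans "Hypothesis tests for differences between subgroups among the Primary Efficacy, Key" Secondary and CGM outcomes, and also tests HbA1c between the stop-frequency groups. Diabetes duration is handled differently: its cut points will "be chosen according to the distribution of the data, but it will be treated as a continuous variable" in the models. No such rule is given for stops.

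SAP section 12 makes no correction for the main Primary and Key Secondary analyses. The subgroup tests come under its rule that for "other analyses, the false discovery rate (FDR) will be controlled using the adaptive Benjamini"-Hochberg procedure.

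Three other provisions matter:

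- Protocol 3.1.2 tells participants to "insert a new sequential infusion set following removal of each prior set until 12 infusion sets have been used". Sets failing in the first 8 hours are replaced and do not count toward the 12.
- SAP 5.2 leaves those early failures out of the primary endpoint. SAP 5.3 includes them in the key secondary endpoint.
- SAP 5.8 limits insulin data to the study pump during wears of the investigational set and requires 20 hours of data for a complete day.

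Neither document defines a manual stop.

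**The concern.** The grouping variable is measured after baseline, over the period in which the outcome occurs. Set failures can enter it in three ways, all conditional on the relevant stops being recorded:

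1. The 12 set changes are fixed in number. A participant whose sets fail early makes them in fewer days, so set-change stops per day go up.
2. Sets failing within 8 hours are replaced on top of the 12, so here the number of stops can rise as well. This bears on the key secondary endpoint only.
3. Handling a suspected failure may itself involve stopping the pump.

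Each pushes participants with more failures toward the high-stop group. A reader of the results would conclude that interrupting the pump goes with set failure, when failure may have produced the stops. The error runs against the device, on a listed secondary endpoint, in a study meant to support a regulatory submission.

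**Working it through.** **The plan's own figure.** The documents give no figure for this subgroup. The sample-size inputs (SAP 4) are 120 participants per insulin type, 12 wears, success 83% against 75%, correlation at most 0.4 and two-sided 5%. They reproduce:

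- Design effect: 1 + 11 × 0.4 = 5.4. Effective n: 1440 / 5.4 = 266.7.
- Null SE: √(0.75 × 0.25 / 266.7) = 0.0265. Alternative SE: √(0.83 × 0.17 / 266.7) = 0.0230.
- Power: Φ[(0.08 − 1.96 × 0.0265) / 0.0230] = 88.9%, or 85.5% with the null SE throughout. The plan states 87%.

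The same inputs are used below.

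**How failures change the rate.** Assume one manual stop per set change and failures spread evenly over 8 to 168 hours, so a failed set lasts on average (8 + 168) / 2 = 88 h = 3.67 days.

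| Failures among 12 sets | Days of wear | Set-change stops per day |
|---|---|---|
| 0 | 12 × 7 = 84 | 12 / 84 = 0.14 |
| 3 | 9 × 7 + 3 × 3.67 = 74 | 12 / 74 = 0.16 |
| 6 | 6 × 7 + 6 × 3.67 = 64 | 12 / 64 = 0.19 |
| 12 | 12 × 3.67 = 44 | 12 / 44 = 0.27 |

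The numerator is 12 in every row. Only the days change.

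**False-positive rate.** I simulated trials in which stopping has no effect on failure. Participant success probabilities are beta-distributed with mean 0.83 and the stated correlation. Other stops are Poisson, with gamma-distributed personal rates (SD half the mean) unrelated to failure. Groups are split at the median stop rate and failure proportions compared by Welch t-test at 5%. Stop rates, the median split and the failure times are my assumptions. Results for n = 120 and correlation 0.4, as ranges over repeated runs of about 1,000 to 3,000 trials:

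| Other stops per day | One stop per set change | Plus one stop per failure |
|---|---|---|
| 0.5 | 14–17% | 84–85% |
| 1 | 8–10% | 33–35% |
| 2 | 6–7% | 11–12% |

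At 0.5 other stops per day, the high- and low-stop groups show failure rates of about 19.4% and 14.8% with set-change stops only, and 23.5% and 10.7% with one further stop per failure. The true difference is zero.

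**Sensitivity.**

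- Correlation 0.1, n = 120: 5–8% with set-change stops only; 34%, 13% and 6% with one further stop per failure.
- Plain Benjamini-Hochberg over 12 tests (six factors by two outcomes, the other 11 null and independent), correlation 0.4: about 3%, 1% and 1% with set-change stops only; about 50%, 8% and 2% with one further stop per failure. The group means do not change.
- Stop rate kept continuous (Spearman test) with no exclusion, correlation 0.4: 17%, 8% and 6%, and 82%, 34% and 12%. Dropping the split does not cure the problem.
- Set-change and failure stops left out of the count: about 4–7% in every setting.

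**The case against.** The strongest reply is that the link is undocumented. No section says that changing a set requires or logs a manual stop. The hyperglycemia procedure in Protocol 1.4 calls for glucose and ketone tests, correction boluses and site contact, and mentions no pump stop. SAP 5.8's limit to wear time might also drop stops made between sets. This stands as a limit on size: the result is conditional, and the column with an added stop per failure rests on assumption alone. It does not dispose of the point. Nothing in SAP 11 excludes such stops, it cites 5.8 only for what makes a day complete, and a stop made before removal would still count.

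It is also fair that the analysis is described as exploratory and that false discovery rate control makes formal rejection rarer. That control presumes valid p-values, however, and does nothing for the estimated difference.

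Four stronger readings are tempting and not supported:

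- *Replacing a failed set adds a stop.* For the primary endpoint it does not. A set failing after 8 hours is one of the 12, so its replacement adds no set change. Only the denominator moves, apart from any stops made in handling the failure.
- *The false-positive rate is 30%, or 99% with an added stop per failure.* Those figures need n = 240, correlation 0.4, 0.5 other stops per day and no adjustment. SAP 6.2 analyses the primary endpoint by insulin type, and SAP 6.3 allows pooling only for the other secondary, exploratory and safety analyses. The correlation of 0.4 is the plan's upper bound.
- *The data-chosen cut point ties the group to the outcome.* It depends on the distribution of stops, not on failures. It is a separate open choice in an unblinded study.
- *Stops should be counted before the study.* Protocol 2.6 provides for "Determination of adherence to Control-IQ use in the 14 days prior to screening based on data from" the personal account, but that describes a different pump and infusion set. Eligibility also requires Control-IQ active at least 85% of that window, which limits heavy interrupters. The endpoint concerns interruption during SteadiSet use.

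**Conclusion.** The concern holds conditionally. SAP 11 uses a stop count that set failures can raise, and then tests set failure against it. If set-change stops are logged, the distortion at n = 120 ranges from negligible (correlation 0.1, or about 2 other stops per day) to a false-positive rate of about 15% (correlation 0.4, 0.5 other stops per day). It becomes large only if failure handling also adds stops and other stops are infrequent. The documents do not settle which case applies. The primary analysis and its power are untouched, so this is a minor point, worth correcting because the correction is cheap.

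**What to change.** In SAP section 11:

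- Define a manual stop.
- Keep the during-study count, but exclude stops within a fixed interval around each set removal, insertion or cartridge change, and stops during a suspected-failure episode. State the interval before the data are examined.
- Enter stop frequency as a continuous variable in the test, as is done for diabetes duration. Use the cut point for display only.

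The exclusion removes the bias; the continuous term only removes the open choice of cut point.

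The cost is SAP wording plus some programming to match stops to changes. Insertion and removal details are already collected through the daily-text questionnaire (Protocol 3.4), and suspected failures through the structured interview (Protocol 1.4). The documents do not say how cartridge changes are time-stamped, so that needs checking. Some unrelated stops that fall near a change will be lost.
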